5.1 Variables

The Cmax, Tmax, AUClast, AUC0-8h, T1/2 PK parameters will be derived for QBW251 plasma concentration data for Day 1, Day 28 if feasible in subset of subjects with extensive PK collection.

5.2 Descriptive analyses

Plasma concentration data for QBW251 will be listed by treatment, subject and sampling time point. Both scheduled and actual times will be included. Descriptive statistics will be provided by treatment and scheduled time point, including the number and frequency (n, %) of concentrations below the lower limit of quantification (LLOQ), which will be summarized as zero and reported as BLQ in the listing. Concentrations will be expressed in mass per volume unit.

Summary statistics will include mean (arithmetic and geometric), standard deviation (SD), coefficient of variation (CV) (arithmetic and geometric), median, minimum and maximum. If zero values occur for the values being summarized due to concentrations below the LLOQ, no geometric mean will be calculated.

Arithmetic mean +/- standard deviations plot of QBW251 plasma concentration will be presented by treatment and using schedule sampling times for Day 1 and 28. An overlaying individual plot will be presented by treatment.

A box plot will be presented by treatment for pre-dose concentrations on Day 1, Day 28, Day 56 and Day 84.

Novartis	Confidential	Page 11 of 20
SAP Amendment 1		Study No. CQBW251B2202
All PK parameters of QBW251	will be listed by treatment and	subject. Summary statistics will

All PK parameters of QBW251 will be listed by treatment and subject. Summary statistics will be displayed by treatment, using the same summary statistics as for the PK concentrations. An exception to this is Tmax, where only median, minimum and maximum will be presented.

All summaries will be based on the PK analysis set, including figures of means. For all listings and figures displaying individual data, all subjects will be shown, but subjects not in the PK population and values marked as unreliable by the PK Scientist will be flagged.

5.3 Statistical model, assumptions and hypotheses

No model-based statistical analysis will be performed for PK.

6 Statistical methods for Pharmacodynamic (PD) parameters

6.1 **Primary objective**

The primary objective of the study is to assess the change from baseline on fibrinogen plasma concentration levels after 12 weeks of treatment with QBW251 compared to placebo.

6.1.1 Variables

The primary estimand, defined below, quantifies a hypothetical effect of 12 weeks treatment that would have been observed if all subjects remained on their treatment for 12 weeks:

- **Target population:** subjects with moderate to severe COPD with features of chronic bronchitis and a history of exacerbations and treated with any of the combinations of LABA, LAMA, or ICS LABA/LAMA, LABA/ICS or LABA/LAMA/ICS along with or without macrolides as background therapy.
- Variables of interest: change from baseline in fibrinogen after 12 weeks of treatment.
- Intercurrent events of interest:
 - 1. Discontinuation of study treatment or study participation before 12 weeks of treatment
 - 2. Intake of antibiotics to treat exacerbations (other than macrolides taken as background medication)
 - 3. Intake of systemic corticosteroids to treat exacerbations.
 - 4. Use of rescue medications before 12 weeks of treatment with study drug or placebo is complete
- **Summary measure:** mean difference between treatment groups (QBW251 compared with placebo).

Novartis	Confidential	Page 12 of 20
SAP Amendment 1		Study No. CQBW251B2202

6.1.2 Descriptive analyses

Summary statistics will be provided by treatment group and visit for fibrinogen and will include arithmetic mean, standard deviation (SD), coefficient of variation (CV), median, minimum and maximum.

6.1.3 Statistical model, assumptions and hypotheses

The primary analysis will include all available data from subjects in the PD analysis set.

The fibrinogen samples taken within 2 weeks after exacerbation or during or after last dose of antibiotics other than chronically administered macrolide would be set to missing if a valid unscheduled assessment did not happen at that time point for the primary analysis.

The primary analysis will be performed using a one-sided test at alpha=0.1 (two-sided 80% confidence intervals) and estimated treatment difference (QBW251-Placebo) at week 12 will be reported along with the associated 80% confidence intervals.

The comparison of QBW251 to placebo will be evaluated by testing the following null hypothesis (H_0) versus the alternative hypothesis (H_1) :

H₀: There is no reduction in fibrinogen from baseline after 12 weeks of treatment in

QBW251 compared to placebo.

H1: There is a reduction in fibrinogen from baseline after 12 weeks of treatment in favor

QBW251 compared to placebo.

The change from baseline in fibrinogen data is assumed to be normally distributed. A MMRM will be fitted to the changes from baseline in fibrinogen for all time points until Day 84 visit including the fixed factors and covariates but are not limited to the following:

- Treatment group
- Visit/Time
- Treatment group by time interaction
- Smoking status
- Baseline fibrinogen value by time interaction.

If normality assumptions are not met, then the fibrinogen data may be log transformed.

Sensitivity analyses:

Novartis	Confidential	Page 13 of 20
SAP Amendment 1		Study No. CQBW251B2202

Supportive analyses:

Supportive analyses will be performed on subjects whose fibrinogen levels or bacterial load collected at the visits during the study based on the different baseline treatments like LABA, LAMA, or ICS using repeated measures model similar to primary analyses.

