Visit Name	Wee	k 8	Week 12			EOS/Early Termination	Safety Follow Up call	Unscheduled 
Visit Numbers 	13	80	140 84 ±3			1999	150	160
Days	5: ±:					91 ±3	114 ±3	
Time (post-dose)	dose	3h	pre-dose	dose	3h	-	-	-
Informed consent								
Informed consent DNA								
Inclusion / Exclusion criteria								
Demography								
Physical Examination						S		S
Body Height								
Body Weight						Х		
Vital Signs		Х	Х		Χ	X		Х
Medical history/current medical conditions								
COPD exacerbation history								
Concomitant medications			Х			X		х
Spirometry 			Х					X 
Smoking status			Х			Х		
Electrocardiogram (ECG)		Х	Х		Х	Х		Х

	Period			Treatment			Treatment Completion Follow-Up	Treatment Completion Follow-Up	Unscheduled
	Visit Name	Weel	8 >	Week 12			EOS/Early Termination	Safety Follow Up call	Unscheduled 
ſ	Visit Numbers 	130	)	140			1999	150	160
	Days	56 ±3		84 ±3			91 ±3	114 ±3	-
ſ	Time (post-dose)	dose	3h	pre-dose	dose	3h	-	-	-

_	_	_		_								
Fibrinogen blood collection 			X									
	Commercially Confidential Information											
Pregnancy test 			Х			Х	Х					
Hematology			Х			Х	Х					
Clinical Chemistry 			Х			X	Х					
Urinalysis 			S			S	S					
					Co	ommercially Confidential Information						
_				_								
High Resolution CT of Chest			X									
Cough And Sputum Assessment Questionnaire (CASA-Q)			x				Х					
St. George's Respiratory Questionnaire (SGRQ)			х				Х					
EQ-5D-3L			Х									
COPD Assessment Test (CAT)			Х									
EXACT-PRO Questionnaire 							Х					

Period			Treatment			Treatment Completion Follow-Up	Treatment Completion Follow-Up	Unscheduled				
Visit Name	Wee	k 8	We	ek 12		EOS/Early Termination	Safety Follow Up call	Unscheduled 				
Visit Numbers 	13	0	1	140		1999	150	160				
Days	5( ±:		84 ±3			91 ±3	114 ±3	-				
Time (post-dose)	dose	3h	pre-dose	dose	3h	-	-	-				
Dispensation of study drug												
Study drug intake at site	Х			Х								
Rescue medication use and record			Х					Х				
e-Diary 			X			X		X				
PK blood collection		X	X		X			X 				
Adverse Events		X										
Serious Adverse Events				Х								
Telephone follow-up												
Safety Follow up Call	·				·		s					

- X Assessment to be recorded in the clinical database or received electronically from a vendor
- S Assessment to be recorded in the source documentation only

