As a consequence, investigational study drug must be permanently discontinued in a subject exhibiting

- an estimated AUC0-24h > 91,700 ng\*hr/ml in association with a reported SAE
- an estimated AUC0-24h > 159,000 ng\*hr/ml even in the absence of any SAE (please see more details regarding this topic on Section 6.5.1.1).

If a female subject of childbearing potential withdraws from the study prematurely, the investigator should recommend her to maintain contraceptive measures for at least 3 days after the last dose of the study drug.

If permanent discontinuation of study treatment occurs, the investigator should make a reasonable effort to understand the primary reason for the subject's premature discontinuation of study treatment and record this information.

The investigator must also contact the IRT to register the subject's discontinuation from study treatment.

If discontinuation occurs because treatment code has been broken, please refer to Emergency breaking of treatment code Section 6.6.3.

Subjects who have their study treatment permanently discontinued should NOT be considered withdrawn from the study UNLESS they withdraw their consent (see withdraw of informed consent section). Where possible, they should return for the assessments indicated in the

assessment schedule in Table 8-1. If they fail to return for these assessments for unknown reasons, every effort (e.g. telephone, e-mail, letter) should be made to contact the subject/predesignated contact as specified in the lost to follow-up section. This contact should preferably be done according to the study visit schedule. If the subject cannot or is unwilling to attend any visit(s), the site staff should maintain regular telephone contact with the subject, or with a person pre-designated by the subject. This telephone contact should preferably be done according to the study visit schedule and at a minimum information on new/ concomitant treatments and adverse events /serious adverse events should be obtained.

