## 12.4.1 **Definition of primary estimand**

The primary estimand, defined below, quantifies a hypothetical effect of 12 weeks treatment that would have been observed if all subjects remained on their treatment for 12 weeks:

- **Target population**: subjects with moderate to severe COPD with features of chronic bronchitis and a history of exacerbations and treated with any of the combinations of LABA, LAMA, or ICS along with or without macrolides as background therapy
- **Variables of interest**: change from baseline in fibringen after 12 weeks of treatment.
- **Intercurrent events of interest:** 
  - 1. Discontinuation of study treatment or study participation before 12 weeks of treatment
  - 2. Intake of rescue medications or intake of antibiotics before 12 weeks of treatment
- **Summary measure:** mean difference between treatment groups (OBW251 compared with placebo).

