## 12.4.3 Handling of missing values/censoring/discontinuations

Estimates of the missing values due to intake of rescue medications or antibiotics will be derived by the model under the missing at random (MAR) assumption. Alternative assumptions may be explored to investigate the robustness of the results under plausible non-missing at random situations.

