## 12.4.4 Sensitivity and Supportive analyses

# Sensitivity analyses

Subjects whose bacterial load or fibringen levels collected at the planned visits regardless of the intake of antibiotics other than macrolide or exacerbated during OBW251 treatment period will be included and analysed using repeated measures model similar to primary analyses. This would allow to assess the robustness of the OBW251 treatment effect on fibringen and bacterial load drop with and without prohibited antibiotics/exacerbation that would be deemed to affect the outcome of interest.

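### The primary estimand assumes every subject stays on treatment, but the primary MMRM takes all available fibrinogen and no readable rule removes values taken after study drug is stopped

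*SAP*

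**What the plan says.** **Estimand.** SAP 6.1.1 says that the primary estimand "quantifies a hypothetical effect of 12 weeks treatment that would have been observed if all subjects remained on their treatment" for 12 weeks, and protocol 12.4.1 defines it in the same way. Both list, as the first intercurrent event, "Discontinuation of study treatment or study participation before 12 weeks of treatment".

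**Data analysed.** SAP 6.1.3 and protocol 12.4.2 carry the same sentence: "The primary analysis will include all available data from subjects in the PD analysis set". The MMRM runs over every time point up to the Day 84 visit.

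**Follow-up after stopping drug.** Protocol 9.1.1 says: "Subjects who have their study treatment permanently discontinued should NOT be considered withdrawn from the study UNLESS they withdraw their consent". It continues: "Where possible, they should return for the assessments indicated in the" schedule in Table 8-1. The row "Fibrinogen blood collection" in that table is marked at Days 28, 56 and 84.

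**Missing data.** Protocol 12.4.3 says: "Estimates of the missing values due to intake of rescue medications or antibiotics will be derived by the model" under MAR, and SAP 6.1.3.1 repeats this. Stopping study treatment is not named.

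**Sensitivity analysis.** Protocol 12.4.4 says that subjects with values "collected at the planned visits regardless of the intake of antibiotics other than macrolide or exacerbated during OBW251 treatment period will be included". That analysis is about antibiotics and exacerbations. The SAP heading for sensitivity analyses has no readable text beneath it.

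**The concern.** A hypothetical estimand for treatment discontinuation needs a data rule: values observed after the event are left out, and the model predicts what they would have been on drug. Here the strategy is declared and the rule is absent. MAR estimation acts only on values that are missing. A fibrinogen value observed after study drug was stopped enters the likelihood as if it were an on-treatment value.

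If the effect wears off after stopping, such values in the QBW251 arm pull the Week 12 difference towards zero and shift its 80% confidence interval. The arms are not fully symmetric. Verified exposure is one ground for permanent discontinuation in protocol 9.1.1. It can arise only on QBW251, because protocol 8.5.2 evaluates PK samples only in subjects given that drug. Two analysts could also treat the same off-drug Day 84 sample differently.

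A second route runs through replacement samples. After a hospitalised exacerbation treated with antibiotics, protocol 8.4.4 takes blood before study drug is restarted. SAP 6.1.3 lets a valid unscheduled assessment stand in for an affected one and does not require the subject to be on drug. The net direction here is not established: such samples can arise in both arms, and protocol 1.1 notes that fibrinogen rises in exacerbations.

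**Working it through.** **1. Does any readable rule remove off-drug values?**

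| Place | What triggers it | Covers stopping drug and staying in the study? |
|---|---|---|
| Protocol Table 6-2 | Standard-of-care treatment of an exacerbation, plus 14 days | No |
| Protocol 12.4.2, SAP 6.1.3 | Exacerbation, or antibiotics other than background macrolide | No |
| Protocol 12.4.3, SAP 6.1.3.1 | Values missing because of rescue medication or antibiotics | No |
| Protocol 9.1.2 | Withdrawal of consent | No |
| PD analysis set and SAP Table 4-1 | Only the informed-consent deviation excludes from the PD set | No |

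The exacerbation rules remove some off-drug values, but only by coincidence.

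**2. Planned numbers.** Protocol 3 and SAP 1.4 give about 100 randomised 1:1, 15% drop-out and about 84 completers. Check: 100 × (1 − 0.15) = 85, which agrees with about 84. Per arm: 84 / 2 = 42. SAP 1.4 also says that the trial was stopped before completion, so the final number is unknown.

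**3. Dilution.** Let *p* be the share of QBW251 Week 12 values taken off drug and *l* the share of the effect lost. Then dilution = *p* × *l*. The documents give neither input. The 15% drop-out figure is not used for *p*, because a subject who leaves the study gives no Week 12 value.

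- *p* = 0: 0%.
- *p* = 0.05 (assumed): 0.05 × 0.5 = 2.5%, and 0.05 × 1 = 5%.
- In whole subjects: 0.05 × 42 = 2.1, so about 2, and 2/42 = 4.76%. Dilution is 2.4% (*l* = 0.5) or 4.8% (*l* = 1).

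**4. Check in a repeated-measures model.** Take a GLS fit with treatment-by-visit means, three visits, exchangeable correlation 0.3, 0.5 or 0.7 (assumed), a true effect of −1, and 2 of 42 QBW251 subjects off drug at the third visit only. Covariates are left out. With no value missing, the GLS means are the arithmetic means:

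- *l* = 0.5: −(40 + 2 × 0.5)/42 = −0.976
- *l* = 1: −40/42 = −0.952

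With the two values set to missing, and MAR true, the estimate is −1.000.

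**5. Price in precision.** Let R² = 2ρ²/(1 + ρ) be the share of third-visit variance explained by the first two visits. The variance ratio, set-to-missing over all data, is

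[(1 − R²)/40 + R²/42 + 1/42] / (2/42).

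| ρ | R² | Standard error ratio |
|---|---|---|
| 0.3 | 0.138 | 1.011 |
| 0.5 | 0.333 | 1.008 |
| 0.7 | 0.576 | 1.005 |

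With no borrowing from earlier visits the bound is √[(1/40 + 1/42)/(2/42)] = 1.012.

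**The case against.** **The strategy is stated and only an operational line is missing.** The estimand sentence is clear, and the heading of protocol 12.4.3 includes discontinuations. This is true of intent. But the text under that heading gives no rule for discontinuation, and the stated rule of using all available data points the other way.

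**Few values can be affected.** An off-drug value needs a subject who stops drug and still attends Day 28, 56 or 84. Subjects who leave the study have the end-of-study assessments (protocol 8), and the readable Table 8-1 shows no fibrinogen there. If the sponsor's decision to stop ended treatment for ongoing subjects, protocol 9.1.5 treats them as prematurely withdrawn. Protocol 4.5 expects few subjects above even the lower exposure threshold. All of this stands, and it is why the range starts at zero.

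**The size is assumed and small.** The 5% share has no source in the documents. The model check is arithmetic on assumed inputs: with complete data it must return 40/42, and the zero bias after the change follows from building in MAR. For scale, 80% power at one-sided 0.10 (assumed, because the sample size section is blacked out) puts the effect at 1.28 + 0.84 = 2.12 standard errors. Dilution of 2.4% to 4.8% is then about 0.05 to 0.10 standard errors, against an 80% interval half-width of 1.28. This limits the urgency but does not reconcile analysis and estimand.

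**The protocol wording would remain, and one case stays open.** An SAP edit narrows a sentence that also stands in the protocol, so the SAP should say so openly. A scheduled sample taken during a temporary interruption (protocol 6.5.1) is not settled by a rule on permanent discontinuation and replacement samples. Both points are fair, and neither removes the gap.

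**Conclusion.** The concern holds. On the readable text, the primary analysis admits fibrinogen values that its own estimand excludes, and protocol 9.1.1 makes such values possible by design. This goes beyond missing detail, because the stated data rule leads to a different quantity. It should be fixed.

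The likely size is modest: no dilution if nobody returns off drug, and 2.4% to 4.8% of the Week 12 difference with 2 of 42 QBW251 values off drug and half or all of the effect lost. The number of off-drug values, the loss of effect and the between-visit correlation are all assumptions. Zero bias after the change also requires MAR to hold. The text missing under the SAP sensitivity heading may be blacked out, but a sensitivity analysis would not define the primary data set.

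**What to change.** In the SAP:

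1. **Section 6.1.3.** For the primary analysis, set to missing any fibrinogen value taken after permanent discontinuation of study drug, and let the MMRM handle it under MAR. Name discontinuation in 6.1.3.1. Report the analysis of all observed values as a sensitivity analysis. Say that this is how the protocol sentence on available data is implemented for the hypothetical estimand.
2. **Section 6.1.3.** State that a sample taken while study drug is stopped, including the pre-restart sample in protocol 8.4.4, is not a valid unscheduled replacement in the primary analysis. State also how a scheduled sample taken during a temporary interruption is handled.

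Separately, reconcile the set-to-missing wording in protocol Table 6-2, the exacerbation dates in protocol 8.4.4 and the rule in SAP 6.1.3. The wording on rescue medication needs the same attention: it is an intercurrent event in SAP 6.1.1 and a cause of missing values in 6.1.3.1, but 6.1.3 has no rule for it. This review does not say which version should apply.

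The cost is two or three sentences before database lock, plus a flag built from dosing start, end and interruption records that protocol 6.5.1 and 6.6.1 already collect. SAP 1.1 describes the SAP as implementing the protocol analysis, and SAP 6.1.1 already expands the protocol's two intercurrent events to four, so the protocol amendment process in 14.1 should not be needed. A few observed values leave the primary model but stay in the sensitivity analysis.

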6.1.3.1 Model checking procedures

Estimates of the missing values due to intake of rescue medications or antibiotics will be derived by the model under the missing at random (MAR) assumption. Alternative assumptions may be explored to investigate the robustness of the results under plausible non-missing at random situations.

6.1.3.2 Graphical presentation of results

Model based plots will be presented for the fibrinogen data.

6.2 Secondary objectives

The key secondary objective is to assess the effect of QBW251 compared to placebo after 12 weeks of treatment on sputum bacterial load.

6.2.1 Variables

The key secondary objective endpoint is:

• Change from baseline in the logarithm of total number of colony forming units (log₁₀CFU/mL) of potentially pathogenic microorganisms in sputum after 12 weeks of treatment.

The bacterial load samples taken 2 weeks after exacerbation (after antibiotic intake is finished) or during or after last dose of antibiotics would be set to missing if a valid unscheduled assessment did not happen at that time point for the primary analysis.

The other secondary pharmacodynamics and efficacy endpoints are as follows:

- Change from baseline in airway wall and lumen parameters along with extent of global and regional air trapping as measured by HRCT after 12 weeks of treatment.
- Change from baseline in FEV1, FVC and FEV1/FVC ratio measured by spirometry after 12 weeks of treatment.
- Subject reported outcomes and exacerbations
 - Changes from baseline in the Euro Quality of Life-5 Dimensions-3 Level (EQ-5D-3L).
 - Changes from baseline in Cough and Sputum Assessment Questionnaire (CASA-Q) domain scores.
 - Change from baseline in COPD Assessment Test (CAT) questionnaire.
 - COPD exacerbations
 - Time to first COPD exacerbation
 - Proportion of subjects with exacerbations

Novartis			Сс	onfic	lenti	al				F	age [·]	14 of 2	20
SAP Amendment 1								Study	No.	CQE	3W25	1B220)2
		0					~	 					

- Annualized rate of exacerbations as defined by EXACT-PRO questionnaire.
- Change from baseline St. George's Respiratory Questionnaire (SGRQ) total and domain scores.

In order to be included in the sputum analysis, a subject must provide a sufficient sputum sample at screening, and/or at baseline and at least one post-baseline visit.

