### 6.2.1.1 Permitted concomitant therapy requiring caution and/or action

Table 6-2 provides an overview of medications permitted under certain conditions, including bronchodilator medications which need to be withheld for certain timeframes prior to spirometry assessments on visit days, and an overview regarding actions to be taken for antibiotics.

Table 6-2 Medications permitted under certain conditions

Rationale/Group	Medication	Prohibition Period	Action Taken
COPD maintenance background therapy	e.g.Vilanterol, Umeclidinium, Indacaterol Glycopyrronium	Hold treatment for 24 hours (+/-2 hours) prior to each FEV 1 / spirometry measurement on visit days for once daily inhaled background therapy and 12 hours (+/-2 hours) for twice daily inhaled background therapy	In case the washout criterion is not fulfilled, reschedule spirometry accordingly. Trough spirometry (-45 min and -15 min assessments) should be done within 24 hours for once daily inhaled background therapy such as LABA/LAMA or LABA/ICS or LABA/LAMA/ICS from dosing on the previous morning and approximately 12 hours for twice daily LABA/LAMA or LABA/ICS or LABA/LAMA or LABA/ICS or LABA/LAMA/ICS from dosing on the previous evening. Otherwise, postpone visit to the next day where washout criteria can be fulfilled
Rescue medication only	Short-Acting Beta-2 Agonists (SABA)	Hold treatment at least 6 hours prior to each FEV 1 /spirometry measurement	If possible, postpone spirometry measurement on the same day until the washout criterion is fulfilled. Trough spirometry (-45 min and -15 min assessments) should be done within 6 hours after last rescue medication intake
Antibiotics for treatment of exacerbations and macrolides as background medication	Antibiotics, e.g. amoxicillin Macrolides, e.g. erythromycin	Systemic and/or inhaled antibiotics are allowed for treatment of acute infections, or are allowed for the treatment of acute exacerbations.	All data will be set to missing during the exacerbation time(time of SoC intake) and for 14 days thereafter with the exception of macrolides for those

Rationale/Group	Medication	Prohibition Period	Action Taken

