## 12.4.2 Statistical model, hypothesis, and method of analysis

The primary analysis will include all available data from subjects in the PD analysis set.

The fibringen samples taken within 2 weeks after exacerbation or during or after last dose of antibiotics other than macrolide would be set to missing if a valid unscheduled assessment did not happen at that time point for the primary analysis.

The primary analysis will be performed using a one-sided test at alpha=0.1 (two-sided 80% confidence intervals) and estimated treatment difference (QBW251-Placebo) at week 12 will be reported along with associated 80% confidence intervals.

The comparison of QBW251 to placebo will be evaluated by testing the following null hypothesis  $(H_0)$  versus the alternative hypothesis  $(H_1)$ :

H0: There is no reduction in fibringen from baseline after 12 weeks of treatment in QBW251 compared to placebo

H1: There is a reduction in fibrinogen from baseline after 12 weeks of treatment in favor of QBW251 compared to placebo.

The change from baseline in fibrinogen is assumed normally distributed. A MMRM will be fitted to the changes from baseline in fibringen for all time points until Day 84 visit including the fixed factors and covariates but are not limited to the following:

- treatment group
- visit/time

- treatment group by visit/time interaction
- smoking status
- baseline fibringen value by visit/time interaction.

If normality assumptions are not met, then the fibringen data may be log transformed.

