# 12.5 Analysis of secondary endpoints

## 12.5.1 Efficacy and/or Pharmacodynamic endpoint(s)

Key secondary pharmacodynamic endpoint:

Change from baseline in the logarithm of total number of colony forming units (CFU/mL) of potentially pathogenic microorganisms in spontaneous sputum after 12 weeks of treatment.

The bacterial load will include all available data from subjects in the PD analysis set and will be analyzed similar to the primary analysis. The bacterial load samples taken within 2 weeks after exacerbation or during or after last dose of antibiotics would be set to missing if a valid unscheduled assessment did not happen at that time point for the primary analysis.

Secondary pharmacodynamic and efficacy endpoints are as follows:

- Change from baseline in airway wall and lumen parameters along with extent of global and regional air trapping as measured by HRCT.
- Change from baseline in FEV1, FVC and FEV1/FVC measured by spirometry after 12 weeks of treatment.

In order to be included in the sputum analysis, a subject must provide a sufficient sputum sample at screening, and/or at baseline and at least one post-baseline visit. The change from baseline in the logarithm of the total number of colony forming units including all different micro-organisms (CFU) and change from baseline in the secondary efficacy including global air trapping and spirometry parameter will be analyzed using the same model as for the primary variable of interest. Contrasts for treatment differences will be provided together with two-sided 80% Confidence Intervals.

All spirometry parameters and HRCT parameters including regional and global air trapping changes will be summarised.

These will be calculated at all time points as specified in the assessment schedule (Table 8-1), and specifically at the primary time point of interest (Day 84) considering placebo as the reference treatment.

Any correlations between changes in air trapping and the lung function parameters measured by spirometry would be explored.

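### The set-to-missing rule for sputum bacterial load has no background-macrolide exception, so read literally it removes permitted macrolide users from the key secondary analysis

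*SAP*

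**What the plan says.** **Key secondary endpoint (sputum bacterial load).** SAP 6.2.1 provides that samples "taken 2 weeks after exacerbation (after antibiotic intake is finished) or during or after last dose of antibiotics would be set to missing", subject to a saving clause: "if a valid unscheduled assessment did not happen at that time point for the primary analysis". Protocol 12.5.1 reads: "The bacterial load samples taken within 2 weeks after exacerbation or during or after last dose of antibiotics would be set to missing". Neither mentions macrolides. The same protocol section says that bacterial load "will include all available data from subjects in the PD analysis set and will be analyzed similar to the primary analysis".

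**Primary endpoint (fibrinogen).** Protocol 12.4.2 restricts its rule to samples taken "during or after last dose of antibiotics other than macrolide would be set to missing". SAP 6.1.3 narrows the exception: "during or after last dose of antibiotics other than chronically administered macrolide would be set to missing".

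**Whole data set.** Protocol Table 6-2 (section 6.2.1.1) states: "All data will be set to missing during the exacerbation time(time of SoC intake) and for 14 days thereafter with the exception of macrolides". It goes on to limit that exception to subjects with bronchiectasis who had been on a stable macrolide dose for three months before screening.

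**Who takes macrolides, and for how long.** Inclusion criterion 6 lets subjects with bronchiectasis as a secondary diagnosis stay on stable macrolides. Table 6-2 requires the dose to stay stable for the whole study, and protocol 6.1.2 continues background therapy from screening to the end-of-study visit.

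**Entry to the sputum analysis.** SAP 6.2.1 requires that "a subject must provide a sufficient sputum sample at screening, and/or at baseline and at least one post-baseline visit".

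**The concern.** A permitted macrolide user is on an antibiotic at every visit. A rule that removes every sample taken during antibiotics, with no exception, therefore removes every sample that subject gives. The protocol admits these subjects on purpose and requires them to be sputum-positive at screening. The analysis of the endpoint closest to the bacterial part of the hypothesis would then leave them out.

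A programmer who finds an explicit macrolide exception in the fibrinogen rule and none in the bacterial-load rule could reasonably take the difference as intended. If the question first arises after unblinding, deciding which subjects belong in the key secondary analysis becomes a post-hoc choice.

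**Working it through.** The plan gives no figure for macrolide use, and its sample-size section is blacked out, so there is no stated figure to reproduce on this point. The check sets the rules side by side and then counts samples.

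**1. The rules compared**

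| Place | Applies to | Macrolide exception | *Within* 2 weeks / 14-day end |
|---|---|---|---|
| Protocol Table 6-2 | all data | stable background macrolide with bronchiectasis | explicit 14 days |
| Protocol 12.4.2 | fibrinogen | any macrolide | *within* present |
| SAP 6.1.3 | fibrinogen | chronically administered macrolide | *within* present |
| Protocol 12.4.4 (sensitivity analysis) | fibrinogen and bacterial load | only non-macrolide antibiotics are at issue | not applicable |
| Protocol 12.5.1 | bacterial load | none | *within* present |
| SAP 6.2.1 | bacterial load | none | *within* absent, no stated end |

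The gap starts in protocol 12.5.1 and the SAP carries it forward. Only the loss of *within* is new in the SAP.

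**2. Samples lost by a continuous macrolide user**

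The sputum row of Table 8-1 is not visible in the public copy, so the schedule comes from the text. Protocol 3.1 gives Day 28, Day 56 and Day 84; protocol 8.3.6 adds screening and baseline.

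- Post-baseline: 3 scheduled, 3 taken during macrolide, 3 − 3 = 0 usable.
- If the rule is also applied before treatment: 5 scheduled, 5 removed, 0 usable. The fallback in protocol section 12, which uses the screening value when baseline is missing, does not help, because that sample is on macrolide too.
- The saving clause does not help either: any unscheduled sample is also taken on macrolide.

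On either count the subject has no post-baseline change from baseline and supplies no response record to the MMRM. With the exception in place, the loss from background macrolide is 0 of 3 (0 of 5).

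**3. What that could cost in precision**

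The share *f* of subjects on background macrolide is not in the documents. The values below are assumptions. With equal loss across arms, unchanged variance and all other subjects observed, the 80% confidence interval widens by 1/√(1 − f):

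- f = 0: 1.00
- f = 5%: 1/√0.95 = 1.03
- f = 10%: 1/√0.90 = 1.05
- f = 20%: 1/√0.80 = 1.12
- f = 40%: 1/√0.60 = 1.29

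**4. The missing *within***

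Protocol 3.1 asks a subject with an exacerbation to return 14 days after the last antibiotic dose for a further sputum sample. Without *within*, the SAP phrase literally describes that sample, while samples taken earlier in the two weeks are not caught by that phrase. Protocol 8.4.4 treats the follow-up as an unscheduled visit, so the same sample could be both the one excluded and the substitute that the saving clause accepts.

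**The case against.** **The word antibiotics plainly means exacerbation treatment.** The parenthesis in SAP 6.2.1 and the words about a last dose both presuppose a finite course, and continuous therapy has no last dose during the study. That is fair for the part of the rule about samples after the last dose. It does not reach the separate part about samples taken during antibiotics, which the sentence does not limit to exacerbation courses.

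**Other text already settles it.** Table 6-2 covers all data, protocol 12.5.1 promises an analysis like the primary one, and the SAP's estimand for fibrinogen (6.1.1) sets background macrolides outside its intercurrent events. This is good evidence that the omission is not intended. It does not override the SAP's specific rule for this endpoint, and general phrases about using all available data cannot restore a value that the rule deletes.

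**The omission may be deliberate, since macrolides act on bacteria.** No passage says so, and Table 6-2 and the sensitivity analysis that names bacterial load both point the other way.

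**Stronger readings that a reader might infer, and that the documents do not support:**

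- *All 5 scheduled samples are certainly lost.* That assumes the rule reaches screening and baseline. It is framed around exacerbations and substitute visits, so 3 of 3 post-baseline is the secure count.
- *At most 20–40% of subjects are affected.* That is the bronchiectasis share expected in protocol 4.1.1. It is a ceiling only if every macrolide user has bronchiectasis. Criterion 6 requires this, but protocol 4.1.1 and 6.1.2 join the conditions with and/or. Those passages must be reconciled; this point does not depend on how.
- *The treatment comparison is biased.* Background macrolide use precedes randomization, and nothing shows a difference between arms.
- *Every sample after any antibiotic course is deleted.* In the protocol rules and SAP 6.1.3, the two-week limit can be read as governing the last-dose part too, in line with Table 6-2. The missing end date is a wording gap, not a demonstrated loss of data.

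**Conclusion.** The concern holds for the wording of the rule. As written, SAP 6.2.1 and protocol 12.5.1 remove all 3 scheduled post-baseline bacterial-load samples of a subject on permitted continuous macrolide, and the subject drops out of the key secondary MMRM. This conflicts with Table 6-2, both fibrinogen rules and the protocol's sensitivity analysis. That analysis lifts the deletion only for non-macrolide antibiotics and exacerbations, so it does not correct the main analysis.

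The result assumes a literal reading and macrolide intake that continues through Day 84. The consequence is reduced precision and a narrower population, not shown bias. The number of subjects cannot be derived and could be zero. The planned headcounts do not help, because SAP 1.4 records a decision to stop the trial before completion. The study is declared non-confirmatory and the primary endpoint is not affected by the missing macrolide exception, so this is a correction to make before database lock, not a threat to the trial's main conclusion.

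The missing *within* and the unstated 14-day end are secondary drafting points, best repaired in the same sentence.

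**What to change.** In a SAP amendment before database lock, replace the bacterial-load sentence in 6.2.1 with:

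> Bacterial-load samples taken during an exacerbation (SoC intake) or during a course of antibiotics other than chronically administered background macrolides, or within 14 days after that intake ends, are set to missing unless a valid unscheduled assessment is available for that time point.

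Use the same macrolide wording and the same 14-day end in SAP 6.1.3. One wording matters because the present exceptions differ: protocol 12.4.2 would also exempt a macrolide given for an exacerbation, such as the clarithromycin named in protocol 8.4.4. Record in the SAP that the new sentence departs from protocol 12.5.1. If the omission was in fact intended, the SAP should say so, give the reason and reconcile it with Table 6-2.

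I would not add a clause letting the follow-up sample override the 14-day window. Protocol 8.4.4 times that visit only approximately, so the sample could fall inside the period that Table 6-2 excludes.

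The cost is one rewritten sentence and one aligned clause, with no new data and no change to treatment or visits. The small downside is that macrolide users stay in the analysis and add some heterogeneity.
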